The proposed study is a single blind randomized, controlled trial (N=144) with two conditions (4-session BA-PC or TAU) that uses an intent to treat design. Following an initial telephone assessment session, all patients who agree to participate and who meet all inclusion criteria will be asked to participate in the study. As depicted in **Figure 2**, all Veterans will complete a baseline assessment. Eligible Veterans will be randomized in equal proportions to one of two conditions (4-session BA-PC or TAU). All Veterans will complete biweekly brief telephone mood assessments for the first 12 weeks. These brief biweekly assessments can also be completed in-person, if they align with another assessment or if the participant prefers to meet in-person. Comprehensive assessments will occur at 6 weeks and 12 (post-treatment), as well as at 24 weeks. After 12 weeks (post-treatment), all participants will be allowed to seek additional psychological treatment, if desired.

Settings

This study will be implemented in four different primary care clinics in VISN 2 (Syracuse VAMC, Canandaigua, Buffalo VAMC's, and Rochester Outpatient clinic). We will seek Buffalo IRB approval as well.

Study Population

Power analyses revealed that a total of 144 Veterans (72 Veterans per group) will need to be randomized to provide 80% power to detect a medium effect of the intervention on depressive symptoms at the 12-week post-

treatment time point, while accounting for a 30% attrition rate across the 12-weeks. Using the previously collected data to give indication of our screening rates and rates of eligibility and consent to enroll in the trial, we expect to be able to recruit 4-5 eligible patients per month across a 33-month recruitment time period resulting in the ability to recruit approximately 165 Veterans. Ultimately, we would need to conduct telephone screens on approximately 335-379 depending on the specific eligibility (38%-43%) rate used from our preliminary study.

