Therapeutic Alliance will be assessed using the Working Alliance Inventory (WAI)¹²⁹. The WAI is a 12-item self-report measure that assesses three different domains of the therapeutic alliance, including agreement on therapeutic tasks, agreement on goals of therapy, and development of a therapeutic bond.

Table 1. Schedule of Assessment Measures

SUBJECTIVE ASSESSMENTS	Time (weeks)							
	0	2	4	6	8	10	12	24
	P	T	T	T	T	T	P	T
1. Symptoms of Depression								
a. PHQ-9*	X	X	X	X	X	X	X	X
2. Intensity of Suicidal Ideation								
a. SSI	X			X			X	X
3. Quality of Life								
a. SF-12	X			X			X	X
b. QLI	X			X			X	X
4. Insomnia Severity								
a. ISI	X			X			X	X
5. Symptoms of PTSD								
a. PTSD-CL	X			X			X	X
6. Symptoms of Anxiety								
a. GAD-7	X			X			X	X
7. Level of Reward/Positive Affect from Experiences								
a. EROS	X			X			X	X
8. Pain								
a. Brief Pain Inventory	X			X			X	X
9. Patient Adherence**								
10. Treatment Receptivity								
a. Client Satisfaction Questionnaire				X			X	

b. BA Acceptability Interview***	X
11. Therapeutic Alliance	X
a. WAI	X
12. Mental Health Treatment	
a. Medication and Treatment History Questionnaire*	X X
c. Medication and Treatment via CPRS*	X X
13. Tobacco Use	
a. Tobacco Use Questionnaire	X

Note. P=in person assessment; T=telephone assessment

*These measures are also given in the initial telephone screening assessment.

**This is calculated after session 2, 3, and 4 of BA-PC

***This measure will be administered at the last BA-PC session and sealed in an envelope to allow for confidentiality and for other research staff to stay blind to condition.

Data Analysis and Statistical Considerations

The data analytic strategy emanates from the primary aim and is in line with the method used to estimate the sample size necessary to adequately test the primary hypothesis. Initial analyses will be conducted using a series of 2 (Condition: TAU vs. BA-PC) vs. 2 (Time: baseline, week 12) repeated measures ANOVAs. The primary analysis will be conducted using the intent-to-treat approach; participants who are randomized will be analyzed according to their assigned group regardless of amount of treatment received. The data will be screened for missing cases, outlier scores, and non-normal response distributions. Assumptions underlying statistical models will be assessed by examining standardized residuals, influence diagnostics and homogeneity of variance (e.g. among groups).

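### The stated 80% power at week 12 holds only under inputs the plan does not give: about 70% for a two-sided unadjusted comparison, 62–79% for the planned repeated-measures ANOVA, and not verifiable for the primary mixed model

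*Combined protocol and SAP*

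**What the plan says.** Study Population gives the sample size: "a total of 144 Veterans (72 Veterans per group) will need to be randomized to provide 80% power to detect a medium effect" on depressive symptoms at the week-12 post-treatment time point, "while accounting for a 30% attrition rate across the 12-weeks". Allocation is equal under Design Overview: "Eligible Veterans will be randomized in equal proportions to one of two conditions". The sentence gives no alpha, sidedness, numerical effect size, SD, correlation or method.

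Data Analysis and Statistical Considerations says that the analysis strategy agrees with the method behind the sample size, without naming that method. It then continues: "Initial analyses will be conducted using a series of 2 (Condition: TAU vs. BA-PC) vs. 2 (Time: baseline, week 12) repeated measures ANOVAs".

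Aim 1 (a, d) sets the primary test as a two-sided test of the group-by-time slope on PHQ-9 in a multilevel model (MLM) with random intercept and slope. Table 1 gives seven PHQ-9 assessments from week 0 to week 12. The Note on Missing Data keeps participants with incomplete outcomes in that model under a missing-at-random assumption.

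**The concern.** The power claim is tied to one time point, and 30% of patients are expected to be lost by then. About 50 completers per arm is the familiar size for a medium effect with a one-sided 5% test; a two-sided test needs 63 or 64. The plan's primary test is two-sided, so the claim and the test do not obviously belong together.

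The 2×2 ANOVA raises a second doubt. Its group-by-time term is a change-score test on patients with both values, and it has less power than ignoring baseline whenever the baseline to week-12 correlation is below 0.5.

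At stake is how a null result would be read. On the unadjusted comparison the chance of missing a medium effect is 30%, and on the ANOVA at a correlation of 0.4 it is 38%, against the 20% that the plan implies.

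**Working it through.** **Inputs.** From the plan: 72 per arm, 30% attrition, 1:1 allocation, 80% power, two-sided primary test, seven PHQ-9 waves to week 12. Assumed, because the plan does not state them: d = 0.5 for a medium effect, alpha 0.05, and the correlations and covariances below. Completers per arm: 72 × 0.7 = 50.4.

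**Reproducing 144.** Normal formula: n per arm = 2(z_alpha + z_beta)² / d².

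- One-sided 5%: 2(1.645 + 0.842)² / 0.25 = 49.5, so 50. Then 50 / 0.7 = 71.4, so 72 per arm and 144 in total. This matches exactly. (With the t distribution it is 51, giving 73 per arm.)
- Two-sided 5%: 2(1.960 + 0.842)² / 0.25 = 62.8, so 63 (64 with the t distribution). Then 63 / 0.7 = 90 or 64 / 0.7 = 91.4, so 92 per arm: 180–184 in total. No match.
- Two-sided 5%, change score: the effective effect is d / √(2(1 − r)). At r = 0.6 this is 0.5 / √0.8 = 0.559, which needs 50.2 completers, and 50.2 / 0.7 = 71.8, so 72. This matches at r of about 0.6.

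**Unadjusted week-12 comparison.** Noncentral t, 50.4 per arm, two-sided 5%: power is 70.0% at d = 0.5 (51% at d = 0.40, 85% at d = 0.60). The effect detectable with 80% power is about 0.56. One-sided 5% at d = 0.5 gives 80.2%.

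**Two-time-point analyses of completers.** Change score (the 2×2 ANOVA interaction): d / √(2(1 − r)). Baseline-adjusted (ANCOVA): d / √(1 − r²). Equal SDs over time are assumed.

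| r | 2×2 ANOVA | ANCOVA |
|---|---|---|
| 0.3 | 56% | 74% |
| 0.4 | 62% | 77% |
| 0.5 | 70% | 82% |
| 0.6 | 79% | 87% |

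Reaching 80% takes r of about 0.60 for the ANOVA and about 0.46 for ANCOVA.

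**Primary MLM slope test.** The SE of the group-by-time coefficient comes from generalised least squares information, summed over dropout patterns, with 72 per arm, seven waves and retention falling linearly to 70%. Power = Φ(δ / SE − 1.96), with a linear group difference reaching δ = 0.5 SD at week 12. The second figure in each cell drops the group term at time 0, so that the arms share a baseline mean.

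| r (weeks 0, 12) | Compound symmetry: as planned / constrained | AR(1): as planned / constrained |
|---|---|---|
| 0.3 | 81% / 93% | 64% / 80% |
| 0.4 | 86% / 94% | 71% / 83% |
| 0.5 | 91% / 96% | 78% / 87% |
| 0.6 | 96% / 98% | 87% / 92% |

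Seven random intercept-and-slope structures were also tried. With baseline variance set to 1, intercept variance was 0.4–0.6, slope variance over 12 weeks 0.2–0.8, intercept–slope covariance 0 to −0.25, and residual variance 1 minus the intercept variance. With d on the week-12 SD, planned power is 72–89%, and 86–93% with the constraint. With d on the baseline SD the same structures give 58–83%, and 74–88% with the constraint.

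**The case against.** The strongest reply is that the 70% belongs to a completers-only unadjusted comparison, which the plan does not name as its primary test. The primary test is an MLM on seven waves that keeps dropouts' data, and under many plausible covariances it exceeds 80%. This stands. A reader might infer that the trial is underpowered for its primary analysis, or that it needs 184 patients. The documents support neither: the MLM result depends on covariances that are not given.

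A reader might also infer that the sponsor used a one-sided calculation. The exact match to 144 is suggestive, not proof, since a change-score calculation gives 144 too. Nor is a correlation of 0.6 a general requirement: about 0.46 is enough for ANCOVA, and roughly 0.3 (compound symmetry) to 0.52 (AR(1)) for the MLM slope.

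The text on Aim 3 (a) refers to a power analysis section that is not in the public file, and the reference list includes a paper on sample size for longitudinal designs with attrition. The missing inputs may therefore exist elsewhere, and their absence here is not evidence of a miscalculation.

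Finally, the ANOVA is labelled initial, so replacing it does not alter the power of the primary test. That is correct. What remains is that the power claim concerns the week-12 time point, the ANOVA is the only analysis built on that time point, and it is the weaker of two ways to use the same data.

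**Conclusion.** The 80% does not hold for a two-sided 5% unadjusted week-12 comparison at d = 0.5 (70%), nor for the planned ANOVA unless the baseline to week-12 correlation reaches about 0.6 (62% at 0.4, 70% at 0.5, 79% at 0.6). Entry at PHQ-9 of 10 or more narrows the baseline range and tends to lower that correlation, but the documents give no figure for it. For the primary MLM the 80% is unverifiable rather than wrong: it can lie above or below 80% depending on the covariance and on which SD scales d. The simplest two-sample route to 144 is one-sided and would conflict with the two-sided test under Aim 1, so the two sections need reconciling. All of this assumes d = 0.5, alpha 0.05 and the stated attrition; the correlation results also assume equal SDs, and the MLM results linear change, linear dropout and missing at random.

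**What to change.** Keep 144.

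1. In Study Population, state alpha, sidedness, the numerical effect with the SD that scales it, the correlation structure and the model behind 144, and reconcile the sidedness with Aim 1. Qualify the claim: about 70% for a two-sided unadjusted week-12 comparison with 50 completers per arm, and about 80% with baseline adjustment if the correlation is at least about 0.46.
2. Replace the 2×2 repeated-measures ANOVA with a baseline-adjusted week-12 contrast. With equal SDs its power is higher at every correlation below 1.
3. In the MLM, constrain baseline PHQ-9 to be equal between arms by dropping the group term at time 0, which randomisation justifies, or use baseline PHQ-9 as a covariate. With d on the week-12 SD, the constraint added about 2 to 16 percentage points in the structures above. The gain depends on the covariance and on the linear trajectory, so it should be quoted with those assumptions.

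The cost is protocol wording, a small change to the model specification, and a less favourable stated power for the unadjusted comparison. No extra patients, visits or data are needed.

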All participants will be asked about depressive symptoms every two weeks for the first 12 weeks over the telephone or in-person. Participants will also be asked to complete more comprehensive telephone and in-person follow-up assessments at 6, 12, and 24 weeks (as shown in Figure 1 and Table 1). During these assessments, participants will be asked to complete the same questionnaires as during the baseline assessment and several additional measures dependent on the assessment as identified in Table 1 focused on patient receptivity and medication/treatment history.

All assessment sessions will be led by research assistants blind to condition and take place primarily (unless requested otherwise) via the telephone except the baseline, 12, and 24 weeks (see Table 1). The 12-week assessment will occur over the telephone if unexpected circumstances prevents the Veteran from being able to come in to the medical center. All research assistants will track any non-study care given to participants as that may be a potential confounding variable to our examination of treatment effect⁸⁸.

At baseline, 12, and 24 week sessions, information will be collected from the medical chart of each participant regarding his/her current medical problem list, medications, engagement with mental health care, including types of interventions that they may or may not have participated in during the study as monitored by the VA electronic medical record system.

Treatment As Usual Condition

TAU will involve the Veteran receiving an appointment with the integrated MHP at their primary care clinic. At this encounter, the MHP can choose to deliver whatever interventions they deem necessary. In addition, the MHP and Veteran can work together to identify whether and when they would like to meet again during the 12-week period of the active portion of the study. As recommended by Freeland et al⁸⁸, it is unnecessary to force the TAU condition to have the same amount of attention unless the purpose is to examine specific and nonspecific effects, which is not the case in this study.

BA-PC Intervention

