Depressive Symptoms will be assessed using the *Patient Health Questionnaire-9 (PHQ-9)*⁹², which is a 9-item self-report questionnaire that assesses the frequency of depressive symptoms over the past two weeks with a specific focus on the symptoms necessary to meet criteria for DSM-IV diagnosis of Major Depressive Disorder. Individuals scoring 10 or above are identified as experiencing moderate symptoms, and those scoring 15 or above are identified as experiencing severe depressive symptoms⁹². Kroenke, Spitzer, and Williams found the PHQ-9 to be both reliable and valid in a sample of 6,000 patients in 8 primary care clinics and 7 obstetrics-gynecology clinics⁹². The total score of the PHQ-9 has also been used as indicative of depression severity and is sensitive to clinical change⁹². It will be used to determine initial eligibility (i.e., inclusion criteria: Veteran scores > 10 on PHQ-9).

It will also be given at the baseline assessment (week 0) to determine status for the stratified block random assignment. The PHQ-9 will also be administered at the other assessment time points as the primary outcome measure for depressive symptoms.

Mania will be assessed using the MINI International Neuropsychiatric Interview modules for mania⁹⁷, commonly used by the BHL to assess symptoms of bipolar. It will be used to determine initial eligibility eliminating those with current manic symptoms.

Psychosis will be assessed using the psychosis portion of the DSM-IV Structured Clinical Interview⁹⁸, as it is often identified as the "gold standard" for assessing psychosis. It will be used to determine initial eligibility during baseline assessment.

Week 0: Baseline Assessment:

Suicidal Ideation Intensity will be assessed using the Beck Scale for Suicidal Ideation (SSI)⁹⁹, which is a 19-item interviewer-administered rating scale designed to assess current intensity of SI by asking about

the patient's specific attitudes, behaviors, and plans to commit suicide. The SSI has demonstrated high internal consistency and concurrent validity with the clinician-administered assessment among both inpatients and outpatients⁹⁹. The SSI has been found to have moderately high internal consistency with Cronbach coefficient alphas at .89 and high interrater reliability with correlations at .98¹⁰⁰. For our primary SI outcome, we will use the total score for the SSI as a continuous measure of intensity of SI.

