The *Client Satisfaction Questionnaire (CSQ)*¹⁰⁹ is an 8-item self-report questionnaire developed to assess patient satisfaction with medical and mental health treatment on a 1 to 4 Likert scale, with higher scores related to a higher level of satisfaction. For example, Veterans will be asked “How would you rate the quality of service you received?” on a four point scale ranging from poor (1) to excellent (4). Using the anchor points of the scale, each item needs to be rated a 3 or 4, yielding a total score of at least 24 or above to demonstrate a good level of satisfaction. The scale has a high degree of internal consistency and correlates highly with therapists’ ratings of perceived client satisfaction¹⁰⁹. Each item rating and the total CSQ score will be used to evaluate participants' satisfaction with the service (i.e., 4-session PC-BA and TAU).

The BA Acceptability Interview is an 18-item interview that was designed for this study to assess the Veteran’s satisfaction with the specific components of the BA-PC intervention (including the patient education handouts), the acceptability of the intervention, and importance of each element of the intervention to the Veteran on a Likert scale. Open-ended questions will be used to elucidate additional comments about each Likert-scaled item. Veterans will also be asked to comment on the format of the intervention (i.e., length and number of sessions) and modality (in-person, internet, or telephone) for the primary care setting (see Appendix 5). This measure will be administered by the research assistant delivering the intervention at the last BA-PC session (to allow the assessment research assistant to stay blind to condition). It will be used to give us additional information on the acceptability of each component of the BA-PC intervention and collect information on future implementation.

Treatment Engagement will be assessed using two variables collected via CPRS record review and supplemented by the Treatment History questionnaire: 1) number of BA-PC and TAU sessions will be summarized (both conditions will likely have a similar upper limit as BA-PC will optimally provide 4 sessions and research on TAU suggests for those patients seen after an initial visit, the average number of sessions is 3) and 2) whether or not the participant had engaged in specialty care as assessed at week 24.

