Aim 2: To evaluate Veteran receptivity and adherence to a 4-session BA-PC. Treatment receptivity will be measured using the CSQ, BA Acceptability Interview, and patient adherence. For the CSQ given at week 6 and week 12, each of the eight items will be summarized by calculating the proportion of patients selecting a 3 or 4 (excellent) within each randomized group. Also, the average summary score and 95% CI at week 6 and 12 will be calculated within the TAU and BA-PC group. For the Likert-scaled items on the BA Acceptability Interview, the mean and 95% confidence interval will be calculated to help summarize participant’s receptivity to BA-PC in primary care. For qualitative questions on the BA Acceptability Interview, two raters will read each participant’s response and will summarize the responses¹¹⁴. Then, the two raters will discuss the summary responses they each identified and will reach a consensus that will inform the format and feasibility of BA-PC. As mentioned in the methods, a measure of patient adherence will be collected at each intervention session (i.e., proportion of the number of goals completed versus the number of goals identified as homework by the interventionist and patient at the end of each session) allowing for an overall patient adherence to be calculated and used as an indirect reflection of patient receptivity.

Aim 3 (a): To evaluate the effectiveness of a 4-session BA-PC in reducing SI

We plan to compare the presence and severity of SI between TAU to BA-PC using MLM for the purpose of generating robust effect size estimates. While p-values are inherently provided by statistical software packages, our emphasis is to calculate means and standard errors at each time point and within each group, thereby focusing on the magnitude of effects, not statistical significance. As alluded to in the Power Analysis section, this study is not necessarily powered for detecting differences in suicidal ideation among groups.

However, SI is relevant to depression and thus will be summarized for exploratory purposes using the most powerful statistical method (e.g. MLM, GEE) given the data characteristics.

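### Assessors described as blind also track non-study care and lead sessions with satisfaction and treatment-history measures that could unblind them; only the BA Acceptability Interview is protected

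*Combined protocol and SAP*

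**What the plan says.** The Design Overview calls the trial single blind, with 144 Veterans randomised to BA-PC or treatment as usual (TAU). The Assessments section places the blind with the outcome assessors: "All assessment sessions will be led by research assistants blind to condition". The same paragraph then states that "All research assistants will track any non-study care given to participants", because such care may confound the treatment effect. It makes no exception for assessors.

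Other relevant statements:

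- **CSQ.** The Data Analysis section, Aim 2, gives its timing: "For the CSQ given at week 6 and week 12, each of the eight items will be summarized". It is summarised in both arms. The one item reproduced under Measures is "How would you rate the quality of service you received".
- **Treatment-history questionnaire.** After screening it is given at weeks 12 and 24 (Measures, Initial Screening Telephone Assessment). Under Treatment Engagement it supplements the chart in counting BA-PC and TAU sessions.
- **Chart review.** It is done at baseline and weeks 12 and 24 and covers the types of intervention received. No role is named for it.
- **Working Alliance Inventory (WAI).** It is listed under the 6, 12 and 24 week assessments. Its visit cannot be read from Table 1 in the text available.
- **BA Acceptability Interview.** The interventionist gives it, "to allow the assessment research assistant to stay blind to condition", and a Table 1 footnote adds that it is sealed in an envelope.
- **Outcomes.** The PHQ-9 is a self-report scale and the primary depression outcome. The SSI is described as a "19-item interviewer-administered rating scale designed to assess current intensity of SI".

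**The concern.** In this trial the Veteran knows which treatment is being received, so the blind protects only the assessor's part of the measurement. That part matters most where the assessor rates or probes, as with the SSI, or reads items aloud by telephone.

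Care tracking sits badly with the blind. TAU is an appointment with the clinic's integrated mental health provider (MHP), while BA-PC is delivered by research assistants. To decide whether an MHP visit counts as study or non-study care, one generally has to know the arm. A conversation about satisfaction with the service, or about treatment received, can also prompt a Veteran to say who provided it.

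If assessors learn the arm, the report could not claim blinded outcome assessment without qualification, and no later analysis could remove whatever bias had entered.

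**Working it through.** No figure in the plan decides this point. The check sets timing, collector and protection side by side.

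| Task or measure | When, after randomisation | Who, as stated | Protection of the blind | Relation to the week-12 outcome |
|---|---|---|---|---|
| Tracking non-study care | No start or end given | All research assistants | None stated | Can precede it |
| CSQ | Weeks 6 and 12 | Session led by blind assessor | None stated | Week 6 precedes it |
| Treatment-history questionnaire | Weeks 12 and 24 | Session led by blind assessor | None stated | Same visit, order not stated |
| Chart review | Weeks 12 and 24 | Not named | None stated | Same visit, order not stated |
| WAI | Not readable here | Listed with the 6, 12 and 24 week assessments | None stated | Cannot be determined |
| BA Acceptability Interview | Last BA-PC session | Interventionist | Separate administrator, sealed envelope | Protected |

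**Outcomes downstream of the documented exposures**

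1. Over the 12-week period the PHQ-9 is taken at weeks 0, 2, 4, 6, 8, 10 and 12. Weeks 8, 10 and 12 follow the week-6 CSQ: three of seven time points. Weeks 0 to 4 precede any CSQ.
2. The SSI is taken at weeks 0, 6, 12 and 24. Weeks 12 and 24 follow the first CSQ. The week-6 SSI shares its visit, in an unstated order.
3. Weeks 2 to 10 are planned by telephone and week 12 in person (Table 1). The assessor therefore has some part in most PHQ-9 administrations before week 12, but the answers remain the Veteran's own.

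**Overlap of roles.** The title of research assistant also covers the BA-PC therapists (Therapists & Therapists Training) and the person who takes the recorder to MHP sessions (Therapist Treatment Fidelity). The plan does not say that the latter is separate from the assessor. It describes no order of measures within a visit and no check of whether the blind held.

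**Illustration only.** The documents give no bias size. Assume:

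- a two-sided test at 0.05 (two-sided is stated; the level is not);
- 72 × (1 − 0.30) = 50.4 analysed per arm;
- a uniform shift of *b* standard deviations between arms caused by assessors.

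For a simple comparison of two means, SE = √(2/50.4) = 0.199 SD, and the false-positive rate is P(|N(*b*/0.199, 1)| > 1.96).

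| Assumed *b* (SD) | *b*/SE | False-positive rate |
|---|---|---|
| 0 | 0 | 5% |
| 0.1 | 0.50 | 7.9% |
| 0.2 | 1.00 | 17.1% |
| 0.3 | 1.51 | 32.5% |

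This is not the planned multilevel test of slopes. It shows only that a small systematic shift would matter if one occurred, and is no evidence that one does.

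**The case against.** The strongest reply is that none of these tasks has to disclose the arm. The CSQ item that is shown is generic. The statement that the scale evaluates both services describes how scores are used; it is not item wording. Session counts separate the arms poorly, since the plan expects a similar upper limit: four BA-PC sessions, against an average of three TAU sessions among those seen after an initial visit. Non-study care, taken literally, excludes the assigned treatment. The PHQ-9 is self-report, and the week-12 visit is in person by default. The SSI analysis (Aim 3) is exploratory and stresses effect sizes over significance.

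Much of this stands, and it rules out several stronger readings that a reader might infer:

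- **That satisfaction, alliance and treatment-history measures all reveal the arm from week 6 on.** Only the CSQ is documented at week 6. Treatment history comes at weeks 12 and 24, and the WAI's visit cannot be read.
- **That the procedure necessarily breaks the blind.** It could; no text shows that it must.
- **That the same assessor follows each Veteran from week 6 to week 12.** Continuity of assessor is not stated.
- **That blind assessors carry out the chart review.** No role is named.
- **That any bias favours BA-PC.** The direction is conjecture.

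The reply does not remove the care-tracking instruction, which covers assessors without exception and is hard to follow without knowing the arm. Nor does it explain why one instrument is guarded for exactly this reason and the others are not.

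**Conclusion.** The concern holds as a risk to the blind, not as a demonstrated failure of it. Before the week-12 visit, two documented tasks could unblind assessors: tracking non-study care and the week-6 CSQ. At the week-12 visit treatment history adds to this, in an order that the plan leaves open. The SSI is the most exposed outcome. The PHQ-9 is less so, because it is self-report, though mostly taken by telephone before week 12.

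The size and direction of any bias cannot be estimated from the documents, and the rates in the illustration rest wholly on assumed shifts. The conclusion assumes that the care-tracking sentence means what it says, and that no unpublished procedure already separates these tasks. A change is worth making because it is cheap and protects a blinding claim on which the report will rely.

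**What to change.** 1. Amend the Assessments section so that blind assessors do not track non-study care or review charts. Assign both to existing staff who know the allocation, for example the research coordinator. The documents do not say whether that role is blind, so this should be stated.
2. At every assessment, have the blind assessor complete the PHQ-9, and the SSI where scheduled, before any other measure.
3. After randomisation, have the CSQ, WAI and treatment-history questionnaire collected by existing unblinded staff who do not deliver BA-PC, or self-completed and sealed at in-person visits. BA-PC therapists should not collect satisfaction or alliance ratings, because answers given to them may be coloured by courtesy. Sealed paper forms do not suit the week-6 telephone visit. The week-24 mode needs settling first: the Assessments text treats it as in person, while Table 1 marks it as telephone.
4. State that assessors neither deliver BA-PC nor handle recordings of TAU sessions.
5. Record the assessor's guess of arm at week 12, after the outcomes are complete, and report it by arm.

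If data have already been collected, report who collected which measure and qualify the blinding claim accordingly.

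The cost is a small logistic burden from reassigning forms among existing staff. No new assessor is needed.
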